### **Analytic Approach for Aim 2 and 3**

Our working hypothesis related to Specific Aim 2 is that differences in self-efficacy, self-management behaviors, goal-setting, and perceived social support will predict changes in pain intensity and coping strategies in youth with SCD. The test of this hypothesis will follow the recommendations for testing "moderated mediation" models described by Bauer, which permits specification of a single equation that furnishes the coefficients necessary for estimating total, direct, and indirect effects in a multilevel mediation model. The single equation is made possible by creating a new outcome variable ("Z") that comprises both the outcome variable of interest ("Y") and mediating variable ("M") simultaneously; the two are distinguished by creating two specification variables ("S") that take on the value of 0 and 1 depending on whether the new outcome variable "Z" represents the mediating variable or outcome variable. The single model is then specified as:

$$Z_{ij} = S_{M_{ij}} (d_{M_{ij}} + a_{ij} X_{ij}) + S_{Y_{ij}} (d_{Y_{ij}} + b_{ij} M_{ij} + c'_{ij} X_{ij}) + e_{Z_{ij}}$$

The model permits the estimation of the indirect effect ( $a_{ij}b_{ij}$ ) as a random effect, and by expressing this random effect as a linear function of a Level 2 variable (in this case, treatment group), it is possible to evaluate group differences in the proposed mediational model (i.e., "moderated mediation"). The models will be specified with "time" as a predictor ("X") of the outcomes pain intensity and coping strategies, with the self-efficacy, self-management behaviors, goal-setting, and perceived social support variables included as mediating variables ("M"). The indirect effect of time will then be specified to be predicted by treatment. As such, this model will allow a test of whether an individual's changes over time in pain outcomes are partly explained by changes in the

hypothesized mediators and whether the strength of this indirect effect varies depending on group.

To address Specific Aim 3, exploratory analysis will be used to examine possible moderators of effects of *iCanCope with Sickle Cell Pain* including engagement with treatment, demographic factors (family income, age, sex), and disease characteristics (SCD pain burden). To assess the moderation effect an interaction term will be included for each separate moderator variable and key predictor of interest (two-way interaction between moderator and group for cross-sectional analysis and three-way interaction between moderator, group and time for longitudinal analysis) in the regression models and test its significance using Wald t-test.

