**5.4. Data to be collected, including long-term follow-up data:**

Outcome data are self-report and will be collected online using the study website (Table 5). All measures have evidence of reliability and validity in youth in this age range, and include the core measures recommended for pain clinical trials. T1 = pre-treatment; T2 = post-treatment (2 months); T3 = follow-up (6 months post-treatment).

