**10.4. Power analysis:**

Based on prior and current study experience, and the pool of available study candidates, we plan to enroll a total of 160 subjects into the pilot RCT. With attrition conservatively estimated at 20% we expect a final sample size of 128. This proposed sample size is based on the following power calculation using preliminary data from investigator experience with prior pain trials and published trials in SCD:

Calculations are based on expected differences in youth pain-related disability and pain intensity. Group sample sizes of 52 and 52 achieve 84% power to detect a difference of 1.0 in pain-related disability between the two treatment conditions, with three assessments, AR(1) covariance structure, SD=4, ICC=0.2, and alpha=0.05. If the difference is 1.5 between treatment arms, then 52 per group achieves 99% power with the same assumptions. For pain intensity, group sample sizes of 49 and 49 achieve 80% power to detect a difference of 0.75 in pain intensity (average over three time points) in a design with 3 repeated measurements having a AR(1) covariance structure, SD=2, ICC=0.2 and 0.05 alpha.

**11. Withdrawal of Subjects****11.1. Anticipated circumstances under which subjects will be withdrawn from the research without their consent:**

The PI may decide to withdraw participants from the study if a family is not able to comply with study procedures or do not understand study instructions.

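### Aim 2 promises a within-youth mediation test, but the printed equation neither centres the mediator nor states the intercept covariance, so the mediator path can be falsely significant

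*Combined protocol and SAP*

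**What the plan says.** The protocol's Analytic Approach for Aim 2 and 3 (section 14.1) adopts a cited method that "permits specification of a single equation that furnishes the coefficients necessary for estimating total, direct, and indirect effects in a multilevel mediation model". Mediator and outcome are stacked into one variable, and the outcome part of the model is printed as "S_{Y_{ij}} (d_{Y_{ij}} + b_{ij} M_{ij} + c'_{ij} X_{ij". X is time, M is each proposed mediator (self-efficacy, self-management behaviours, goal-setting, perceived social support), and the outcomes are pain intensity and coping. On the comparison of arms it says: "The indirect effect of time will then be specified to be predicted by treatment". The purpose is given as: "this model will allow a test of whether an individual's changes over time in pain outcomes are partly explained by changes in the" mediators.

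Section 5.4 fixes the visits: "T1 = pre-treatment; T2 = post-treatment (2 months); T3 = follow-up (6 months post-treatment".

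Four things are not stated: how M is prepared before it enters the equation, whether each youth's mean of M enters separately, whether d_M and d_Y may covary, and which test is applied to b or to the indirect effect. The method is cited as reference 84, but the printed reference list ends at 72.

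**The concern.** All youths follow the same three planned visits, so time varies only within a youth. The path from time to the mediator (a) is therefore a within-youth path, and the path from mediator to pain (b) has to be one as well if a·b is to be an indirect effect of time. As printed, M_ij carries two things: the youth's stable level and the departures from it at each visit. Stable differences between youths cannot transmit an effect of time. Randomising the arm does not balance them within the b path either, because mediator level is not randomised.

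At stake is the mechanism conclusion. Youths who are more confident at every visit may also have less pain at every visit. An analysis that takes this for within-youth mediation could credit self-efficacy or social support with a role it does not have.

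**Working it through.** **1. The plan's own figure.** Section 10.4 gives no power or error rate for Aim 2. For pain intensity, an Aim 2 outcome, it says "group sample sizes of 49 and 49 achieve 80% power to detect a difference of 0.75 in pain intensity", with SD 2, AR(1), ICC 0.2 and three visits. The SD of the three-visit mean is 2 × √(3 + 4×0.2 + 2×0.04)/3 = 2 × √3.88/3 = 1.313. The SE of the difference is 1.313 × √(2/49) = 0.265. Then 0.75/0.265 = 2.83, and power is Φ(2.83 − 1.96) = 80.7%. The figure reproduces with a two-sided 5% test.

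**2. Inputs for the check.**
- From the documents: n = 128 ("With attrition conservatively estimated at 20% we expect a final sample size of 128") and T = 3 visits.
- Assumed: M and pain scaled to variance 1; stable between-youth shares ρ_M and ρ_Y of 0.2 to 0.5; correlation r of the stable parts of 0 or −0.3 to −0.5; exchangeable errors.
- The documents give no mediator ICC and no value of r. The 0.2 in 10.4 is paired with AR(1), so using it as a stable share is also an assumption.
- True within-youth b = 0.

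**3. Closed-form approximation** (variance components taken as known).
- Within-youth information per youth: W = (T−1)(1−ρ_M)/(1−ρ_Y)
- Variance of a youth's mean of M: v = ρ_M + (1−ρ_M)/T
- Between-youth information: B = v/[ρ_Y + (1−ρ_Y)/T]
- Between-youth slope: b_B = r√(ρ_M ρ_Y)/v
- Independent intercepts: b tends to b_B × B/(B+W), with SE 1/√(n(W+B))
- Covarying intercepts: b rests on W alone, so its true SD is 1/√(nW), while the reported SE stays near 1/√(n(W+B))

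Take ρ_M = 0.5, ρ_Y = 0.2, r = −0.5. W = 2×0.5/0.8 = 1.25. v = 0.5 + 0.5/3 = 0.667. B = 0.667/0.467 = 1.429. b_B = −0.158/0.667 = −0.237.
- Independent: b = −0.237 × 1.429/2.679 = −0.126; SE = 1/√(128×2.679) = 0.054; |z| = 2.34; rejection Φ(2.34 − 1.96) ≈ 65%.
- Covarying: true SD = 1/√(128×1.25) = 0.079 against a reported 0.054; rejection 2Φ(−1.96×0.054/0.079) ≈ 18%. This does not depend on r.

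With ρ_M = ρ_Y = 0.2 and r = −0.3: W = 2, B = 1, b = −0.129/3 = −0.043, SE = 0.051, and rejection is about 13%. With covarying intercepts the true SD is 1/√256 = 0.0625, and rejection is about 11%.

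**4. Simulation of the stacked model** (maximum likelihood, n = 128, three visits, 300 runs per cell; ICCs 0.2 to 0.5).

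| Form of the model | Mean b | 5% Wald test of b rejects |
|---|---|---|
| M as printed, independent intercepts, r = −0.3 to −0.5 | −0.04 to −0.14 | 16–72% |
| M as printed, covarying intercepts | about 0 | 9–20% |
| M person-mean-centred | about 0 | 4–7% |

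In the covarying row the reported SE is 0.050–0.054 against an empirical SD of 0.059–0.083, even at r = 0. Further runs of the ρ_M = 0.5, ρ_Y = 0.2 cell agree with step 3. With independent intercepts, rejection was 5.2% at r = 0 and 66.9% at r = −0.5. With covarying intercepts, 400 runs at r = −0.5 gave SE 0.053, SD 0.081 and Wald rejection 21.7%. Likelihood-ratio tests with covarying intercepts rejected in 3–7% overall.

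**5. From b to the indirect effect.** A false b gives a false a·b only where the mediator changes over time, and a false group difference only where that change differs by arm. One simulation assumed a treatment shift of 0.75/2 = 0.375 SD in both pain and mediator, ICCs of 0.2 to 0.7 and r of −0.3 to −0.5. The treatment-related indirect effect was falsely significant in 5–76% (independent), 4–14% (covarying) and 2–7% (centred). The 0.375 comes from a pain figure; applying it to the mediator is an assumption.

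**The case against.** The strongest reply is that the plan is silent on centring and does not choose against it. A general equation need not show how its variables are prepared, and the cited method may cover both centring and the covariance. It is not in the printed reference list, so this cannot be checked. That stands: a reader might infer that the sponsor has decided to enter the mediator raw, and the documents do not show that. But nothing in them supplies the missing step, and the printed equation taken alone does not deliver the within-youth test that is claimed.

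Second, a reader might take the largest rates as the expected error rate of Aim 2. The documents do not support this. Those rates need independent intercepts, and estimating M and pain jointly, with a·b as a random effect, sits more naturally with intercepts that covary. They also need an assumed between-youth correlation. With covarying intercepts, stable differences do not bias b. What remains is a standard-error problem of the Wald test, which a likelihood-ratio test avoids. Section 14.1 names a Wald t-test for Aim 3 only and no test for Aim 2. This too stands, and it is why the two cases are kept apart.

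Third, a reader might infer that any effective treatment must move the mediator, so that a false b always becomes a false mechanism. The treatment could work by another route, so this does not follow.

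Finally, the Aim 2 hypothesis, that differences in the mediators predict changes in pain, is worded less strictly within-youth than the sentence on what the model tests. It is that sentence the equation has to support.

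**Conclusion.** The concern holds as a mismatch between claim and specification. The text promises a within-youth test; the equation has no centring or person-mean term, and the intercept covariance is left open. Each way of fitting it as printed has a fault. With independent intercepts, b is pulled towards the between-youth association, unless that association is nil. With covarying intercepts, b is sound but its usual Wald test is too liberal, whatever the correlation.

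The direction of these results is firm, because the closed form and the simulations agree. The exact rates are not, since the mediator ICCs and the mediator–pain correlation are assumptions. The point bears on a mechanism aim of a pilot trial. The Aim 1 feasibility and GEE efficacy analyses are unaffected. It should be settled before the Aim 2 analysis is run, and it does not put the trial's main comparison in doubt.

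**What to change.** In the outcome part of the equation in section 14.1:
- replace M_ij by M_ij minus that youth's own mean over visits;
- add the youth's mean as a Level 2 predictor of d_Y;
- form a·b, and its difference between arms, from the within-youth b only;
- state the covariance structure of the random effects, including whether d_M and d_Y may covary, and name the test for b and for the indirect effect.

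This needs a few lines of text and one derived variable, and no new data. The standard error of b becomes larger because between-youth information is no longer used: by the formulas above, from 0.051 to 0.0625 with both ICCs at 0.2, and from 0.054 to 0.079 with mediator ICC 0.5 and pain ICC 0.2. Relative to the covarying-intercept model little real precision is lost, since these larger values are close to the spread that b actually shows there.

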#### **14.2. Quality control procedures for collected data.**

The PI will supervise the study coordinator in collating and storing data and overseeing the integrity of study records. Data will be maintained on a network server with password protection and daily backup of data performed. The primary source of data will come from online assessments conducted on the REDCap website provided through ITHS at UW. REDCap has extensive security precautions appropriate for the storage of PHI. REDCap was developed specifically around HIPAA-Security guidelines and is recommended for use by researchers. In 2010 the Institute of Translational Health Sciences Biomedical Informatics Core (ITHS BMI) began supporting an installation of REDCap (Research Electronic Data Capture), which is software specifically designed for electronic data capture (EDC) for clinical trials. REDCap features include differentiated user roles and privileges, user authentication and authorization security, electronic signatures, SSL encryption, and comprehensive auditing to record and monitor access and data changes. PIs can configure REDCap User Rights and Data Access Groups to provide granular study data access to authorized study personnel. Access to servers is restricted to authorized ITHS BMI support personnel. The servers are located on ITHS-owned hardware in a secure server room at the University of Washington. This server room meets the technical requirements for HIPAA compliance and hosts other servers containing Protected Health Information (PHI). The Operating System of each server will be kept fully patched and firewalled in accordance with UW Medicine Information Security Policy. All identifying information will be removed from all electronic data, thus protecting the identities of participating families. Data will be kept for a minimum of seven years.

To ensure the accuracy of the data the following processes will be implemented:

- The study coordinator will check all data from REDCap questionnaires for completeness.
- REDCap will be exported directly to SPSS statistical software, to ensure the participant's responses are accurately entered into the database used for analyses. This will be secure and stored locally at Seattle Children's.

**iCanCope Program-** The Toronto site will be responsible for maintaining the study iCanCope smartphone app, which will be used for some online data entry by study participants. The iCanCope app will be hosted at the Centre for Global eHealth Innovation at University Health Network (UHN). Data stored on the iCanCope server will be protected from data corruption as per policies of the UHN data center. Regular backups will be performed in order to prevent against unrecoverable corruption issues. All processes will be PHIPA compliant.

## **15. Confidentiality**

### **15.1. Procedures to secure the data and/or specimens during storage, use, and transmission:**

All participant data will be coded with a unique identification number, thus ensuring the subject's identity as a participant in this study will remain confidential. The research records will be kept confidential and protected health information will be safeguarded as required by Seattle Children's IRB and HIPAA regulations. The research staff and Seattle Children's IRB will be allowed to inspect the information collected from this study. Data collection online through REDCap will also be private and confidential. REDCap was developed specifically around HIPAA-Security guidelines and is recommended for use by researchers. In 2010 the Institute of Translational Health Sciences Biomedical Informatics Core (IHS BMI) began supporting an installation of REDCap (Research Electronic Data Capture), which is software specifically designed for electronic data capture (EDC) for clinical trials. REDCap features include differentiated user roles and privileges, user authentication and authorization security, electronic signatures, SSL encryption, and comprehensive auditing to record and monitor access and data changes. PIs can configure REDCap User Rights and Data Access Groups to provide granular study data access to authorized study personnel. Access to servers is restricted to authorized IHS BMI support personnel. The servers are located on IHS-owned hardware in a secure server room at the University of Washington. This server room meets the technical requirements for HIPAA compliance and hosts other servers containing Protected Health Information (PHI). The Operating System of each server will be kept fully patched and firewalled in accordance with UW Medicine Information Security Policy.

No personally identifying health information is stored in the app. Users are given unique login IDs and use nicknames as usernames in the app. All participant data will be coded with a unique identification number, thus ensuring the subject's identity as a participant in this study will remain confidential. The research records will be kept confidential and protected health information will be safeguarded as required by Seattle Children's IRB and HIPAA regulations. The research staff and Seattle Children's IRB will be allowed to inspect the information collected from this study. All contact information and identifying data will be stored in a secure computer file within [name] research lab at SCRI. Participant contact information and PHI will be sent to SickKids Toronto and it would be stored in a secure, password protected computer file within [name] lab at SickKids.

### **15.2. Location where the data and/or specimens will be stored:**

All contact information and identifying data will be stored in a secure, password protected computer file within the PI's research lab at Seattle Children's. Participant contact information and PHI will also be stored in a secure, password computer file within [name] lab at SickKids for purposes of setting up the login information for the app and website and for programming the iCanCope 'optional' modules.

### **15.3. Length of time data and/or specimens will be stored:**

Data will be kept for a minimum of seven years

### **15.4. Individuals with access to data and/or specimens:**

Only the research staff and Seattle Children's IRB will be allowed to inspect the information collected from this study.

**15.5. Process for the transmission of data and/or specimens outside Seattle Children's:**

**15.5.1. List of data and/or specimens that will be transmitted:**

Participant contact information is being sent to Sickkids Toronto so they can provide login information to the website and app. Seattle will also send information about ASWS and PROMIS depression score to Sickkids Toronto for programming the iCanCope 'optional' modules.

**15.5.2. Individual(s) who will transmit data:**

Study coordinators at Seattle Children's and SickKids Toronto will send this information in a secure email. Study staff at Seattle Children's will comply with the Electronic Communication of PHI policy and procedures.

**16. Provisions to Monitor Data to Ensure the Safety of Subjects**

**16.1. Plan to periodically evaluate the data collected regarding both harms and benefits to determine whether subjects remain safe:**

N/A

**16.2. Data reviewed to ensure safety of subjects:**

N/A

**16.3. Safety information collection procedures:**

N/A

**16.4. Frequency of cumulative data review:**

N/A

**16.5. Conditions that trigger an immediate suspension of the research:**

N/A

**17. Use of Social Media**

**17.1. Types of social media to be used and how:**

We will be using Instagram and Facebook for recruitment purposes only. It will be used to share the study flyer, information and provide a link to the REDCap referral form where potential participants may contact the SCRI study team.

**17.2. Measures in place to protect the privacy or confidentiality of subjects:**

Community members may voluntarily disclose their information on social media if they choose to because the comment section will be open to the public. Their participation in the study may also be disclosed if they choose to disclose that information. Participants will be encouraged to use the online referral form or email the study team instead of Instagram to contact the study team so that we can protect their privacy.

**17.3. Types of communications that will be submitted to the IRB for review:**

All Instagram and Facebook study flyers will be uploaded for IRB review.

**17.4.** If user-generated content will be active, how it will be monitored and what actions will be taken to ensure subject safety and study integrity:

N/A

**18. Research Related Injury**

**18.1.** Available compensation in the event of research related injury:

N/A

**19. Recruitment Methods**

**19.1.** When, where, and how potential subjects will be recruited:

At Emory/CHOA, The Hospital for Sick Children, and Connecticut Children's Medical Center, the potential subjects are recruited at their Sickle Cell clinics. Local study staff will mail a study introduction letter and follow up with a phone call. Study staff may also make an in-person clinic visit during the patients' appointments. Once eligibility is confirmed and documented on the eligibility checklist, consent/assent will be obtained by a trained member of the research team. Consent/assent will preferably be obtained in person, or by telephone if the patient is not able to come to the hospital. If the patient is not able to come to the hospital in person to sign the consent forms, the research staff will review the forms over the phone with the patient and provide instructions to send the signed consent form back either by mail, fax, or SickKids secure file transfer.

At Seattle and all other sites: Child participants will be receiving care from one of our study sites. Potential participants will be introduced to the study and given a flyer about the study by their provider. If interested in being contacted, their provider will send the potential participant's contact information to the study team at Seattle Children's. The potential participant will be contacted over the phone by Seattle Children's to screen for eligibility. If eligible, consent forms will be emailed to participants and a consent call will be set up for a future time.

Additional participants will be identified via the websites and social media outlets (Facebook and Instagram) of sickle cell disease community organizations such as [REDACTED]. These participants will be able to view a study flyer, and if they are interested in participating, they may fill out the referral form through REDCap with their contact information and a few preliminary eligibility questions. They may also contact SCRI staff directly if they have questions about the study. SCRI staff will then contact these potential participants and screen them for eligibility over the phone. If eligible, consent forms will be emailed to participants and a consent call will be set up for a future time.

**19.2.** Steps that will be taken to protect potential subjects' privacy interests:

Participants will be asked by someone known to them if interested in participating before contact information is shared with the coordinating center for approach.

Participants recruited from the community will have information stored and transmitted securely through REDCap.

**19.3.** Sources of subjects:

Potential subjects will be identified by their clinic provider at participating sites. Additional participants will be recruited from sickle cell disease community organizations.

**19.4.** Methods that will be used to identify potential subjects:

Potential participants will be introduced to the study and given a flyer about the study by their provider at the clinic. If interested in being contacted, their provider will send the potential participant's contact information to the Seattle Children's Research Institute study team using either a secure and direct fax line to the study staff or submitting a REDCap form online. The contact information will be sent to Seattle Children's using the referral form (see attached Referral Form document). Providers will only need to check Yes or No to the following eligibility criteria: age 12-18 years, has pain from sickle cell disease, able to speak and read English, and has access to the Internet. Study staff at SCRI will then screen for further eligibility during a phone call with the potential participants. Identifying potential subjects will rely on the identification by the patients' care providers.

Potential participants will also be able to contact the SCRI study team through the social media advertisement.

